7.2. Statistical considerations for interim analyses

NA

8. CHANGES FROM PLANNED ANALYSES (AMENDED 03-DEC-2020)

The calculation of GMT/GMCs ratio and their 90% CI between RSVPreF3 dTpa and RSVPreF3_Placebo in terms of RSV-A Nab titers and RSV IgG antibody concentrations at Screening, Day 8 and Day 31 pooled for all subjects will be removed from analyses plan. We will report adjusted GMT/GMC ratio and their 95% CI which is generated from ANCOVA model.

Adjusted GMT/GMC ratio with both 90% CI and 95% CI which are generated from ANCOVA model will be reported in terms of RSV-A Nab titers and RSV IgG antibody concentrations.

The calculation of GMCs ratio and their 90% CI between RSVPreF3 dTpa and dTpa_Placebo groups in terms of antigens PT, FHA, PRN, D and T will be added at Day 31 pooled for all RSV formulation.

Lab assay cut-off of RSV-A Nab titers for humoral immunity will be reported by using both IU/ml (International units/millilitre) and ED60.

9. NON-STANDARD DATA DERIVATION RULES AND STATISTICAL METHODS

The following sections describe additional derivation rules and statistical methods which are not presented in section 10.1

9.1. Data derivation

9.1.1. Immunogenicity (*Amended 03-DEC-2020*)

For a given subject and given immunogenicity measurement, missing or non-evaluable measurements will not be replaced. Therefore, analysis will exclude subjects with missing or non-evaluable measurements.

- For the within-group assessment, the descriptive analysis performed for each assay at each timepoint will exclude subjects with a missing or non-evaluable measurement.
- For the between group assessments, statistical model will be fitted based on the subjects having a result at both the baseline and the considered timepoint.

Following table shows all antigens will be analysed at considered time point for different treatment groups

Immunogenicity Endpoints		Statistical Analysis Methods
RSVPreF3	
 • RSVPreF3 IgG antibody concentration, and • Neutralizing antibody titers against RSV-A 	
(US and ex-US data to be considered pooled, then separately for the first vaccination, US and ex-US data to be pooled for second vaccination)
 
For the data collected for the second vaccination, the humoral immune response of RSV PreF3 will be summarized based on 2 dose levels (60 and 120 µg) from the first vaccination.
 
 • GMCs/GMTs and their 95% CI will be tabulated and represented graphically • Geometric mean of ratios of antibody titer/concentrations at each individual post-vaccination time point over pre-vaccination (screening) will be tabulated with 95% CI • Antibody titer/concentration will be displayed using reverse cumulative curves pooled. • The kinetics of GMT/GMCs will be plotted as a function of time for subjects with results available at all time points pooled. • A further exploratory between-groups of RSVPreF3 dTpa and RSVPreF3 alone in terms of RSV-A Nab titers and RSV IgG antibody concentration, analysis will be performed at Day 8 and Day 31 post 1st dose using an ANCOVA model by including study groups, country, age category, and level of antibodies at Screening as covariates

Immunogenicity Endpoints	Statistical Analysis Methods
Boostrix (dTpa)	
 Booster response to PT Booster response to FHA Booster response to PRN 
For the subjects received RSVPreF3 dTpa and subjects received dTpa placebo (US and ex-US data to be considered pooled, then separately for the first vaccination) (US and ex-US data to be considered pooled for the second vaccination)
 
 Booster response rates for PT, FHA and PRN (with exact 95% CI) will be calculated by group for US and ex-US pooled formulation and separately. The GMT/GMCs ratio and their 90% CI between RSVPreF3 dTpa and dTpa placebo in terms of anti-PT, anti-FHA, anti-PRN will be calculated between Day 31 post vaccination over Screening for US and ex-US pooled data and separately. For 1st vaccination, a further exploratory between-groups analysis will be performed at Day 31 using an ANCOVA model by including study groups, country, age category, and level of antibodies at Screening as covariates For Boostrix booster response to antigens PT, FHA and PRN, the two-sided standardized asymptotic 95% CI for the group differences in the percentage of subjects with a booster response to each antigen in the RSVPreF3 dTpa vaccine group and (minus) the dTpa Placebo vaccine group at Day 31 post vaccination will be calculated for US and ex-US pooled data and separately
	
 Anti-D concentration Anti-T concentration 
 The percentage of subjects with anti-D antibody concentrations ≥ 1.0 IU/mL by ELISA and the percentage of subjects with anti-T antibody concentrations ≥ 1.0 IU/mL by ELISA (with exact 95% CI) will be calculated by group for US and ex-US pooled data and separately The GMT/GMCs ratio and their 90% CI between RSVPreF3 dTpa and dTpa placebo in terms of anti-D, anti-T will be calculated at Screening and Day 31 post vaccination for US and ex-US pooled data and separately. Protection rate (percentage of subjects with antibody concentrations ≥ 0.1 IU/mL by ELISA) for antigens D and T, the two-sided standardized asymptotic 95% CI for the group differences in the percentage of subjects with antibody concentrations ≥ 0.1 IU/mL in the RSVPreF3 dTpa vaccine group and (minus) the dTpa Placebo vaccine group at Day 31 post vaccination will be calculated for US and ex-US pooled data and separately.

9.1.1.1. Laboratory assays cut-offs for humoral immunity (Antibody determination) (Amended 03-DEC-2020)

A seronegative subject is a subject whose antibody titre is below the cut-off value of the assay. A seropositive subject is a subject whose antibody titre is greater than or equal to the cut-off value of the assay. The cut-off tests for immunogenicity evaluation will be as per following:

Sample	Component	Method	Unit	Cut-off*	ULOQ
Serum	Respiratory Syncytial Virus A Ab neutralizing	NEU	ED60 and/or IU (international unit)	18 for ED60 56 for IU	ED60 : 123535 IU : 217400
Serum	Respiratory Syncytial Virus PreF3 Ab.IgG concentration	ELI	ELU/mL	25	251 769
Serum	Bordetella pertussis.Filamentous Hemagglutinin Ab.IgG	ELI	IU/mL	2.046	3182.397
Serum	Bordetella pertussis.Pertactin Ab.IgG	ELI	IU/mL	2.187	6313.300
Serum	Bordetella pertussis.Pertussis Toxin Ab.IgG	ELI	IU/mL	2.693	883.559
Serum	Corynebacterium diphtheriae.Diphtheria Toxoid Ab.IgG	ELI	IU/mL	0.030	59.545
Serum	Clostridium tetani.Tetanus Toxoid Ab.IgG	ELI	IU/mL	0.037	116.428

Ab = antibody; ELI = Enzyme-linked immunosorbent assay (ELISA); IgG = immunoglobulin G; RSV = respiratory syncytial virus; ED60 = serum dilution inducing 60% inhibition in plaque forming units; IU/ml = International units/milliliter, IU= International units

Assay cut-off and unit might be subject to change before starting of testing (e.g. in case of requalification, revalidation or standardisation). In this case, this will be documented in the clinical report.

9.2. Statistical Method

NA

10. ANNEXES

10.1. Business rules for standard data derivations and statistical methods

This section contains GSK Vaccines' standard rules for data display and derivation for clinical and epidemiological studies. These rules will be applied along with those detailed in section 9 (additional study-specific rules).

10.1.1. Attributing events to vaccine doses

The dose relative to an event is the most recent study dose given to a subject prior to the start of a given event.

If an event starts on the same day as a study dose, the relative dose will be derived from the additional information provided in the CRF using the contents of the flag indicating if the event occurred before or after vaccination. If 'after vaccination' is selected, the relative dose for the event will be the one administered on the start day of the event. If 'before vaccination' is selected, the relative dose for the event will be the dose prior to this one.

10.1.2. Handling of missing data

10.1.2.1. Dates

When partially completed dates (i.e. with missing day or month) are used in calculations, the following standard rules will be applied:

- A missing day will be replaced by 15
- A missing day and month will be replaced by June 30th.

The following exceptions apply:

- Adverse event start dates with missing day:
 - If the event starts in the same month as at least one of the study doses, the contents of AE.AESTRTPT (the flag indicating if the event occurred before or after vaccination) will be used to complete the date. If 'after vaccination' is selected, the imputed start date will match the first (or only) study dose given during that month. If 'before vaccination' is selected, the imputed date will be one day before the first (or only) study dose given during that month.
- Adverse event start dates with missing day and month:
 - If the event starts in the same year as at least one of the study doses, the contents of AE.AESTRTPT (the flag indicating if the event occurred before or after vaccination) will be used to complete the date. If 'after vaccination' is selected, the imputed start date will match the first (or only) study dose given during that year. If 'before vaccination' is selected, the imputed date will be one day before the first (or only) study dose given during that year.

All other cases of incomplete AE or concomitant medication/vaccination start date will follow the standard rules above.

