## CONFIDENTIAL

209141 (RSV MAT-011)  
Protocol Amendment 6 Final

Epoch	Epoch 001	Epoch 002 (Vaccination 1)			Epoch 003 (Follow-up 1)		Epoch 004 (Vaccination 2)				Epoch 005 (Follow-up 2)
Type of contact	Screening	Visit 1	Visit 2	Visit 3	Phone Contact 1		Visit 4	Visit 5	Phone Contact 2	Visit 6	Phone Contact 3
Time points	Day -7 to Day 1	Day 1	Day 8	Day 31	Day 181	Day 181 to -7 before 2 nd vaccination	Day -7 to Day of 2 nd vaccination	From 12 up to 18 months post 1 st vaccination	Day 8 post 2 nd vaccination	Day 31 post 2 nd vaccination	Day 181 post 2 nd vaccination
Sampling time points	Pre-Vacc 1	Vacc 1	Post-Vacc 1	Post-Vacc 1	Post-Vacc 1	Pre-Vacc 2	Pre-Vacc 2	Vacc 2	Post-Vacc 2	Post-Vacc 2	Post-Vacc 2
Recording of AE leading to withdrawal		●	●	●	●			●	●	●	●
Recording of serious AE 	●	●	●	●	●		●	●	●	●	●
Recording of pregnancies		●	●	●	●		●	●	●	●	●
Recording of concomitant medications/vaccinations 		●	●	●	●		●	●	●	●	●
Record any intercurrent medical conditions			●	●	●		●	●	●	●	●
Screening conclusion	●										
Investigator sign-off on eCRF before analysis	●			●	●					●	●
COVID-19 eCRFs log page							●	●	●	●	●
Study conclusion primary study					●						
Study conclusion extension											●

Vacc: vaccination

- is used to indicate a study procedure that requires documentation in the individual eCRF.
- is used to indicate a study procedure that does not require documentation in the individual eCRF

1 Date of birth (month and year or year only, as per local regulations), race, ethnicity and childbearing potential (if subject not of childbearing potential, the specific reason should be documented in the eCRF) (see Section 12.6.1.1.1 for more detail).

2 Physical examination including resting vital signs (blood pressure, heart rate and respiratory rate, temperature) measured after at least 10 minutes of rest.

Screening: Physical exam, vital signs (blood pressure, heart rate and respiratory rate, temperature), and weight, height and BMI will be recorded in the eCRF.

Visit 1: History directed physical exam will be performed and the vital signs will be recorded in the eCRF

**CONFIDENTIAL**209141 (RSV MAT-011)  
Protocol Amendment 6 Final

Visit 2 Physical examination will be performed only if deemed necessary by the investigator. If performed, only vital signs (blood pressure, heart rate and respiratory rate) will be required recorded in the eCRF

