#### 7.2.1.2.1. Study group and treatment number allocation

The target will be to enrol approximately 500 eligible subjects (250 in the US and 250 ex-US). Of these, 250 subjects will be randomized to 5 study groups in a 1:1:1:1:1 ratio using SBIR in the US, and the other approximately 250 will also be randomized to 5 study groups in a 1:1:1:1:1 ratio using SBIR ex-US.

Allocation of the subject to a study group at the investigator site will be performed using a randomisation system on internet (SBIR). The randomisation algorithm will use a minimisation procedure by treating study formulation (US and ex-US) as a stratification factor, and age at the time of vaccination (18-32 or 33-45 years of age) and center as minimization factors.

When SBIR is not available, please refer to the SBIR user guide or the Study Procedures Manual (SPM) for specific instructions.

After obtaining the signed or witnessed/thumb printed and dated ICF from the subject and having checked the eligibility of the subject, the study staff in charge of the vaccine administration will access SBIR. Upon providing the formulation (US or ex-US), age, centre and the subject identification number, the randomisation system will determine the study group and will provide the treatment number to be used for each dose.

The number of each administered treatment must be recorded in the eCRF on the Vaccine Administration screen.

Note that as soon as the target number of approximately 250 subjects in the US or 250 subjects ex-US has been reached, the enrolment will be frozen for this formulation.

**CONFIDENTIAL**209141 (RSV MAT-011)  
Protocol Amendment 6 Final

Since the second dose vaccination is open study, the treatment number will be allocated for each subject sequentially at each centre.

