4.2.2.1. Excluded subjects from Per-protocol analysis set

A subject will be excluded from the PPS analysis under the following conditions

Table 4 Elimination code and condition (Amended 03-DEC-2020)

Code	Condition under which the code is used	Visit (timepoints) where the code is applicable	Applicable for analysis set/endpoint
800	Fraudulent data	All	All
900	Invalid informed consent	All	All
1030	Study vaccine not administered at all	All	Safety, immunogenicity
1040.Vx+*	Administration of concomitant vaccine(s) forbidden in the protocol	All	Immunogenicity
1050	Randomisation failure	All	Immunogenicity
1060	Randomisation code was broken	All	Immunogenicity
1070**	Subjects got vaccinated with the correct vaccine but containing an incorrect volume	All	Immunogenicity
1070**	Vaccination not according to protocol (site of injection, route of administration, wrong replacement of study treatment administered)	All	Immunogenicity
1070**	Study treatment not prepared as per protocol (e.g. reconstitution)	All	Immunogenicity
1070**	Other deviations related to wrong study treatment/administration/dose	All	Immunogenicity
1070**	Study treatment administered while contraindication	All	Immunogenicity
1080	Vaccine temperature deviation	All	Immunogenicity
1090	Expired vaccine administered	All	Immunogenicity
2010	Protocol violation (inclusion/exclusion criteria) DOB – VAC – 18-45 years	All	Immunogenicity

CONFIDENTIAL

209141 (RSV MAT-011)
Statistical Analysis Plan Amendment 4

Code	Condition under which the code is used	Visit (timepoints) where the code is applicable	Applicable for analysis set/endpoint
2150	Failure to report safety events per protocol	All	Safety
2040.Vx+*	Administration of any medication forbidden by the protocol	Visit 2/Day 8 Visit 3/Day 31 Visit 4 Visit 6	Immunogenicity
2040.Vx+*	Device, excluded by the protocol, was administered	Visit 2/Day 8 Visit 3/Day 31 Visit 6	Immunogenicity
2050.Vx+*	Intercurrent medical conditions which are exclusionary as per protocol	Visit 3/Day 31 Visit 4 Visit 6	Immunogenicity
2060.Vx+*	Concomitant infection related to the vaccine which may influence immune response	Visit 2/Day 8 Visit 3/Day 31 Visit 6	Immunogenicity
2070.Vx+*	Concomitant infection not related to the vaccine but may influence immune response	Visit 2/Day 8 Visit 3/Day 31 Visit 4 Visit 6	Immunogenicity

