10.1.3. Data derivation**10.1.3.1. Age at vaccination in years**

When age at vaccination is to be displayed in years, it will be calculated as the number of complete calendar years between the date of birth and the date of vaccination. For example:

DOB = 10SEP1983, Date of vaccination = 09SEP2018 -> Age = 34 years

DOB = 10SEP1983, Date of vaccination = 10SEP2018 -> Age = 35 years

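### The SAP's 15th-of-the-month rule for missing AE start days can move an in-window event outside Day 1-30 and date it after the visit that reported it

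*SAP*

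**What the plan says.** SAP Amendment 4, section 10.1.2.1, opens with a general rule: "When partially completed dates (i.e. with missing day or month) are used in calculations, the following standard rules will be applied". The rules are "A missing day will be replaced by 15" and "A missing day and month will be replaced by June 30th".

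AE start dates have two exceptions. If the day is missing and the event's month contains a study dose, the before/after-vaccination flag is used, and an event flagged as after vaccination is dated to the dose. If day and month are both missing, the same is done when the event's year contains a dose. Then: "All other cases of incomplete AE or concomitant medication/vaccination start date will follow the standard rules above". The section does not limit the imputed date to the visit or contact that recorded the event.

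SAP 5.3.1 counts unsolicited AEs over the day of vaccination plus 29 days, and SAP 10.1.3.8 numbers the vaccination day as Day 1, so the window is Day 1-30. Protocol Table 4 allows Visit 3 at 30 to 45 days after Visit 1.

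On age, Protocol Table 3, footnote 1, collects "Date of birth (month and year or year only, as per local regulations". SAP 10.1.3.1 says of age that "it will be calculated as the number of complete calendar years between the date of birth and the date of vaccination". Code 2010 in SAP Table 4 reads "Protocol violation (inclusion/exclusion criteria) DOB – VAC – 18-45 years".

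**The concern.** A 30-day window usually runs past the end of the month in which the dose was given. The exception stops at that month-end, so a day-missing event in the following month is set to the 15th even when the window, and often the visit that reported the event, has already passed. The result is an impossible onset date, and an event that belongs in the window is left out of it.

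Unsolicited AEs after each dose are a primary safety endpoint (SAP Table 1), so the rule applies twice per subject in the extension.

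The general opening sentence does not exempt birth dates. If a birth date is held as a year only, the 30 June rule could shift derived age by one year. That matters at the 18 and 45 eligibility limits and at the 32/33 boundary used for the age category.

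**Working it through.** The plan states no figure for the date rule. Its only related figure is the worked age example in SAP 10.1.3.1 (born 10 September 1983; vaccinated 9 or 10 September 2018). Year difference, minus 1 if the birthday has not been reached, returns 34 and 35 as stated.

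**One case.** Dose on 5 March is Day 1. Day 30 is 3 April and Day 31 is 4 April. An AE on 1, 2 or 3 April is in the window. If Visit 3 on 4 April records it only as April, no dose falls in that month and the date becomes 15 April. That is 26 + 15 = 41 days after the dose, so Day 42: 12 days past the window and 11 days after the visit.

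**General case.** Let the dose be on day d of a month with L days. Day 30 falls on day n = d + 29 - L of the next month, so n is also the number of in-window onset days in that month. The 15th lies outside the window when n is 14 or less.

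- L = 31: dose days 3 to 16. L = 30: days 2 to 15. L = 29: days 1 to 14.
- Onset days moved out, per month of doses: 1 + ... + 14 = 105.
- All in-window onset days in the next month: 1 + ... + 29 = 435.
- Share: 105/435 = 24.1%. Over 12 months and 366 dose dates, 1,260 of 5,220.
- Against all in-window onsets (366 x 30 = 10,980): 1,260/10,980 = 11.5%. The other 5,760 onsets share the dose month; flagged as after vaccination, they go to the dose date and stay in the window.
- Dose dates affected: 14 x 12 = 168 of 366.

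**Dated after Visit 3.** A visit on Day 31 falls on day n + 1 of the next month, so the 15th is later when n is 13 or less: 91/435 = 20.9% (1,092 of 5,220). With the visit 31 days after the dose, the figure is 936/5,220 = 17.9%. With the visit 45 days after, it is zero.

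**Day and month missing.** Dose on 10 December 2019, AE on 5 January 2020 recorded only as 2020. No dose falls in 2020, so the date becomes 30 June 2020, Day 204. The allowed window for Phone Contact 1 (165 to 195 days) closed on 22 June.

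**Opposite direction.** Dose on 20 March; Day 30 is 18 April. A serious AE on 25 April (Day 37) recorded as April becomes 15 April, Day 27, and is counted in the window.

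**Birth dates (secondary).** Suppose the year only is held and 30 June is imputed.

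- Born 10 December 1973, vaccinated 15 November 2019: true age 45, derived 46.
- Born 20 January 2002, vaccinated 2 March 2020: true age 18, derived 17.
- Born 1 March 1985, vaccinated 15 November 2019: 34 both ways.

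With uniform birthdays, the chance of a one-year error is min(f, 1 - f), where f is the fraction of the year elapsed at vaccination: at most about 50%, on average 25%. With ages uniform over the 28 years from 18 to 45, about 1 wrong age in 28 crosses a limit: at most 50%/28 = 1.8%, on average 25%/28 = 0.9%, of women with year-only birth dates.

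**The case against.** The trigger may be rare. Diary cards cover unsolicited AEs to Day 31 (Protocol Table 3, footnote 6), and source data are verified on an ongoing basis (Protocol 12.4.8). An event reported on 4 April as starting in April has four possible days and is easily queried. No document says how often days are missing. This stands and limits the practical size, but does not make the rule right when it is used.

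The 24.1% could be read as the share of AEs lost. It is not. It applies only to in-window AEs that lack a day and start in the month after the dose; among all day-missing in-window AEs it is 11.5%. A reader might also infer that every dose on the 1st to 15th is affected. The exact range depends on month length: a dose on 15 February 2020 has Day 30 on 15 March, so the imputed date stays in the window.

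A reader might infer a net undercount. The documents do not support that. In-window events are moved only outward, but serious AEs are collected past Day 31 and included in the unsolicited summaries (SAP 10.1.2.4), so later ones can be moved in. The net bias cannot be calculated from what is given.

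The most tempting stronger reading is that the rule makes ages wrong and so excludes eligible women from the per-protocol set. That is inference. The AE sentence does not cover birth dates, no text says that any site collects year only, and none says that code 2010 is assigned from an imputed birth date. About 27 of 28 wrong ages would trigger nothing, and an error can equally admit a woman of 17 or 46. For month-and-year birth dates, the 15th can err only when vaccination falls in the birth month. What remains is a gap: the SAP does not say how a partial birth date is handled, and code 2010 lacks the asterisk that requires individual review.

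**Conclusion.** The AE point holds as a defect in a stated rule. For doses in roughly the first half of a month, an in-window AE in the following month with no recorded day leaves the primary safety window. With Visit 3 near Day 31, it is in most such cases dated after the visit that reported it. The size is 24.1% of day-missing in-window AEs that start in the month after the dose, or 11.5% of all day-missing in-window AEs. These figures assume dose dates uniform over a leap-year cycle and onsets uniform over Day 1-30. The after-visit share runs from 20.9% for a Day 31 visit to zero at 45 days after the dose. The effect on reported AE rates is unknown because the frequency of partial dates is unknown.

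The age point is conditional and secondary. If year-only birth dates occur and are imputed, at most about 1.8% of those women could be wrongly given code 2010, assuming uniform ages. The change is worth making because it is cheap and removes impossible dates from a primary safety endpoint.

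**What to change.** In SAP 10.1.2.1, for an AE with a missing start day (or day and month) in a month (or year) without a dose, impute the earliest date compatible with the recorded month or year and the before/after flag, and never later than the visit or contact that recorded it. In the 5 March case this gives 1 April, Day 28. A cap at the visit alone would not suffice: 4 April is Day 31, still outside the window. The earliest date also matches the SAP's own same-month convention of dating such events to the dose. Cap concomitant medication start dates at the recording visit in the same way.

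For code 2010 and the age_cat covariate (SAP 5.2.2.1), use the age entered in SBIR at randomisation, which Protocol 7.2.1.2.1 already requires ("Upon providing the formulation (US or ex-US), age, centre and the subject identification number"), not an age from an imputed birth date.

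The cost is SAP wording and derivation code, and the SBIR age must be available in the analysis data. The downside is that AE rates may rise slightly. The earliest date is the conservative choice and does not prevent false inclusion: a serious AE on 25 April recorded as April, after a 5 March dose, would go to Day 28 and be counted, where the present rule gives Day 42.
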